2.1.6 Potential Risks

Side effects of oral iron supplementation include constipation, nausea, diarrhea, abdominal pain, vomiting, heartburn, flatulence and dark stools.^{8,35} When compared to placebo in randomized controlled trials, ferrous sulfate had an increased incidence of gastrointestinal (GI) side effects with an OR 2.32 (95% CI 1.74-3.08). The proportion of patients with GI side effects was 35% (range 10-90%) in the ferrous sulfate arms compared with 22 % (range 0-69%) in the placebo arms. The most common side effects were constipation, nausea and diarrhea with pooled estimates of incidence of 12%, 11% and 8% respectively.³⁵ Additional side effects included abdominal pain, vomiting, heartburn, flatulence and dark stools. There did not appear to be a significant association between dose and GI side effects. These side effects can have a significant impact on adherence with studies reporting up to 40% non-adherence and need to be carefully documented.³⁶ A recent study specifically developed a one page side effect questionnaire in patients on oral iron supplementation and was able to distinguish GI symptoms between participants on oral ferrous sulfate and placebo.³⁷ A modification of this questionnaire will be used in the current study.

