5.3.4 Adherence and Dose Modification

This is a pragmatic trial. Adherence will be documented by patients by providing a patient diary (see Supporting Documents) which shows the days on which they are supposed to take oral iron. This will be provided in a paper format. The research team will remind the patient to fill in their patient diary at 4 and 8 weeks. At the 12 week visit, the patient will be instructed to bring in their patient diary and pill bottle. A pill count will also be done to confirm adherence.

It is anticipated that ~ 30% of patients may not tolerate oral iron. The patient adherence diary instructions (see Supporting Documents) can be referred to for simple instructions (under point # 5) if the patient is having mild symptoms with the oral iron. Side effects may improve over the initial 1-2 weeks of oral iron. However, in some cases, patients may not be able to tolerate oral iron. Patients will be instructed to follow their planned schedule as prescribed. If they continue to have symptoms, patients will be instructed to step down in frequency (e.g. from daily to every other day; from every other day to two times per week; from two times per week to once per week) and to record how frequently they are able to take oral iron.

If patients are unable to take the oral iron at all, they will be continued to be followed as long as they are willing to continue and do not meet any criteria for withdrawal. Please refer to Section 10. Criteria for withdrawal from study.

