7.2 Secondary outcome assessments

Feasibility

1. Proportion of eligible patients consenting to participate

$$\frac{\# \text{ meeting eligibility criteria} - \# \text{ in whom consent not obtained}}{\# \text{ meeting eligibility criteria}}$$

2. Proportion of consenting patients receiving the allocated treatment

consenting to treatment - # not administered allocated treatment
consenting to treatment

3. Proportion of treated patients completing 4 week and 12 week laboratory tests

completing 100% of 4 week and 12 week lab tests
consenting to treatment

4. Proportion of treated patients completing 4 week, 8 week and 12 week side effect questionnaire

completing 100% of 4 week, 8 week and 12 week side effect questionnaire
consenting to treatment

5. Proportion of treated patients completing 4 week, 8 week and 12 week FACIT-fatigue scale

completing 100% of 4 week, 8 week and 12 FACIT-fatigue scale
consenting to treatment

6. Proportion of treatment doses taken as per protocol based on pill count

$$\frac{\text{total # of doses} - \text{# of missed doses}}{\text{total # of doses}}$$

7. Proportion of treated patients taking at least 90% of their prescribed doses

$$\frac{\text{# of patients taking at least 90% of prescribed doses}}{\text{total # of treated patients}}$$

8. Proportion of treated patients requiring a step down in therapy

$$\frac{\text{# of patients requiring step down in therapy}}{\text{total # of treated patients}}$$

Clinical/Safety

9. Hemoglobin increment at 4 and 12 weeks is defined as the 4 or 12 week hemoglobin value minus the baseline hemoglobin value

10. Proportion with complete hemoglobin response defined as hemoglobin greater than or equal to 120 g/L in women; and 130 g/L in men at 4 weeks and 12 weeks

11. Change in reticulocyte count at 4 and 12 weeks defined as the 4 or 12 week reticulocyte count minus the baseline reticulocyte count

12. Change in ferritin, serum iron and TSAT at 12 weeks defined as the value at 12 weeks minus the baseline value

13. Quality of life (FACIT-fatigue scale) at 4, 8 and 12 weeks

14. Proportion with side effects and type of side effects at 4, 8 and 12 weeks as determined by the oral iron side effect questionnaire
15. Proportion of patients who stop taking oral iron due to side effects at 4 and 12 weeks

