9.1.2 Expected adverse events with ferrous sulfate

Side effects of oral iron supplementation include constipation, nausea, diarrhea, abdominal pain, vomiting, heartburn, flatulence and dark stools.^{8,35} When compared to placebo in randomized controlled trials, ferrous sulfate had an increased incidence of gastrointestinal (GI) side effects with an OR 2.32 (95% CI 1.74-3.08). The proportion of patients with GI side effects was 35% (range 10-90%) in the ferrous sulfate arms compared with 22% (range 0-69%) in the placebo arms. The most common side effects were constipation, nausea and diarrhea with pooled estimates of incidence of 12%, 11% and 8% respectively.³⁵ Additional side effects included abdominal pain, vomiting, heartburn, flatulence and dark stools.

Overall, the risk to patients enrolled in this study is anticipated to be low, as 1) patients with IDA would normally be treated with oral iron; 2) patients with a prior history of intolerance to oral iron will be excluded; 3) exclusions include patients with baseline gastrointestinal disease such as inflammatory bowel disease; 4) patients will be monitored for side effects throughout the study; and 5) side effects stop immediately with stopping oral iron with no long term sequelae.

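### Item 14 reports side effects only visit by visit, so intolerance followed by step-down or stopping may not show at later visits, and no cumulative per-patient measure is defined

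*Combined protocol and SAP*

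**What the plan says.** Sections 3.4 and 7.2 (item 14) define the side-effect outcome as "Proportion with side effects and type of side effects at 4, 8 and 12 weeks as determined by the oral iron side effect questionnaire". It is a separate proportion at each of three visits.

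Section 5.3.4 sets out what happens to patients with symptoms: "If they continue to have symptoms, patients will be instructed to step down in frequency", with daily to every other day as the first example. It adds "If patients are unable to take the oral iron at all, they will be continued to be followed", provided they are willing and meet no withdrawal criterion. It also states "It is anticipated that ~ 30% of patients may not tolerate oral iron". Section 9.1.2 says that "side effects stop immediately with stopping oral iron with no long term sequelae".

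Related outcomes stand apart from item 14:
- Item 8 is the proportion stepping down. Section 3.4 limits it to step-down caused by side effects; the formula in 7.2 does not.
- Item 15 is the proportion stopping iron because of side effects, at weeks 4 and 12.
- Section 5.4.2.1 lists a side-effect questionnaire at week 1. Item 14 does not use it, and Appendix C does not mark it.

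Section 8.2 gives an intention-to-treat analysis and a per-protocol set. It has no rule for how item 14 treats patients who have stepped down or stopped.

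**The concern.** Limiting side effects is half of the rationale for every-other-day dosing (section 2.2) and part of the secondary objective (section 3.2). Item 14 measures symptoms on whatever schedule the patient is following at the visit. A daily patient who could not tolerate the regimen may by week 8 or 12 be on the experimental schedule or off iron, and may then report no symptoms. The patients who tolerated the assigned regimen worst can therefore drop out of the affected count while still being observed. No outcome counts a patient once for having failed to tolerate the regimen to which they were randomized. At stake is the tolerability estimate that the pilot hands to the definitive trial.

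**Working it through.** **Arm size.** The plan gives no figure for item 14; Table 2 supplies only the number of patients. For true difference 0, SD 5, margin 5, one-sided 5% and 90% power, n per arm = 2 × (1.645 + 1.282)² × 5²/5² = 17.1, rounded up to 18. That is 36 in total, and 36/0.70 = 51.4, rounded up to 52, or 26 per arm. This reproduces the plan.

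**Patients exposed to the problem.** If the anticipated 30% applies equally to both arms (an assumption), 0.30 × 26 = 7.8 per arm and 0.30 × 52 = 15.6 overall could be on a reduced schedule or off iron when item 14 is scored.

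**Items 8, 14 and 15 do not give a per-patient rate.** Take hypothetical rates of 20% symptomatic at a visit, 30% stepped down and 10% stopped. With complete overlap the combined rate is 30%; with none it is 20 + 30 + 10 = 60%. The three proportions fit anything between.

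**Possible effect on the arm contrast.** Visit proportion = ever-affected proportion × (1 − share of those affected who are symptom-free by the visit after step-down or stopping).

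Inputs:
- Daily arm ever affected: 35%, from section 2.1.6: "The proportion of patients with GI side effects was 35% (range 10-90%) in the ferrous sulfate arms". This is a pooled figure with a wide range, not a rate for this trial.
- Every-other-day arm ever affected: not in the documents; assumed 20% to 35%.
- Symptom-free shares: not in the documents; varied.
- The questionnaire records current symptoms: assumed.

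If 25%, 50% or 75% of those affected are symptom-free by the visit, the daily figure is 0.35 × 0.75 = 26.25%, 0.35 × 0.50 = 17.5% or 0.35 × 0.25 = 8.75%. The table gives daily minus every-other-day, in percentage points. Column heads show the symptom-free share in the daily arm / the every-other-day arm.

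| Every-other-day ever affected | Ever-affected difference | 25% / 0% | 50% / 0% | 50% / 25% | 50% / 50% | 0% / 25% |
|---|---|---|---|---|---|---|
| 20% | +15 | +6.25 | −2.5 | +2.5 | +7.5 | +20 |
| 25% | +10 | +1.25 | −7.5 | −1.25 | +5 | +16.25 |
| 30% | +5 | −3.75 | −12.5 | −5 | +2.5 | +12.5 |
| 35% | 0 | −8.75 | −17.5 | −8.75 | 0 | +8.75 |

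For example, in the 25% row under 50% / 25%: 17.5 − 0.25 × 0.75 × 100 = 17.5 − 18.75 = −1.25. The contrast can shrink, change sign or grow. The distortion is largest when resolution differs between the arms.

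**What the documents say about the share.** Section 9.1.2, taken literally, implies 100% for patients who stop. Section 2.1.6 also gives 22% with gastrointestinal side effects on placebo. If everyone left iron and reverted to that rate, prevalence would fall from 35% to 22%, a share of (35 − 22)/35 = 37%. For step-down without stopping, the documents give no figure.

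**The case against.** The strongest points on the other side are these.

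- **Recall period.** The questionnaire is in Supporting Documents, which were not supplied. If it asks about the whole interval since the last contact, a patient who had symptoms and then stepped down is still counted at the next visit. This stands as a condition on the point. Such recall would remove most of the problem at week 4, but a patient who stopped before week 4 could still read as unaffected at weeks 8 and 12.
- **Partial relief.** Section 2.1.6 says "There did not appear to be a significant association between dose and GI side effects", and section 9.1.2 speaks of stopping, not of reducing frequency. This stands: the effect is surest for patients who stop completely.
- **Missing, not misclassified.** Patients whose therapy is escalated complete no further assessments (5.4.2.2). Section 10.1 ends study procedures on withdrawal, and 10.2 seeks only quality of life and laboratory values. These patients are absent from item 14 and are not counted as free of side effects. This stands, and it narrows the point to patients who step down or stop and remain in follow-up.
- **Intolerance is captured elsewhere.** Items 8 and 15 report it, and adverse events are sought at each contact. This stands in part: the information is not lost, but no listed outcome joins it per patient. Nothing says that item 8 will be pooled across arms; equally, nothing says that it will be shown by arm.
- **Legitimate measure.** In a pragmatic trial, symptom prevalence by randomized arm, with step-down as part of the strategy, is a valid quantity. This stands. Whether a cumulative measure should rank above it is a matter of choice.

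A reader might go further and infer that by week 12 the daily arm would look the better tolerated. Taking 35% affected and 30% stepping down or stopping, all from among the affected and all fully relieved, leaves (9.1 − 7.8)/26 = 5%. The documents do not support this. It assumes complete relief from step-down as well as stopping, ignores the 22% placebo rate, and applies to the daily arm a 30% that section 5.3.4 states for patients in general. Any reversal also needs every-other-day rates that the documents do not contain.

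**Conclusion.** The point holds in a limited form. Item 14 has no cumulative counterpart, and later-visit proportions can miss patients who failed to tolerate the assigned regimen, then stepped down or stopped, and stayed in follow-up. The conclusion rests on the questionnaire recording current symptoms, or at least not reaching back to baseline. The later-visit arm contrast can be distorted in either direction, and its size is unknown; the table illustrates the mechanism and is not an estimate. A reader might also infer that the bias always pulls the arms together; the last column of the table shows that it need not.

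This is a secondary outcome of a feasibility pilot. The primary outcome and the sample size are unaffected. The consequence is a tolerability estimate that could mislead the design of the definitive trial.

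**What to change.** Add beside item 14 a cumulative per-patient outcome, analysed by randomized arm: any side effect on any scheduled questionnaire (weeks 1, 4, 8 and 12), or step-down or stopping because of side effects, by week 12. Show its two components separately: any symptom, and step-down or stop.

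Keep the visit-specific proportions. Present each with the regimen being taken at that visit and the number of missing questionnaires. Report items 8 and 15 by arm, and restrict item 8 in section 7.2 to step-down due to side effects, as section 3.4 already does. Reconcile Appendix C with section 5.4.2.1 on the week 1 questionnaire, and state the questionnaire's recall period.

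The cost is outcome wording and one table; the data are already collected. The drawback is that a cumulative measure includes transient early symptoms, which section 5.3.4 says may improve over the first 1–2 weeks, and does not show resolution. That is why the visit-specific rows stay. No change to the step-down rule is proposed.

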3.4 Secondary Outcome Measures

Feasibility

1. Proportion of eligible patients consenting to participate
2. Proportion of consenting patients receiving the allocated treatment
3. Proportion of treated patients completing 4 week and 12 week laboratory tests
4. Proportion of treated patients completing 4 week, 8 week and 12 week FACIT-fatigue scale
5. Proportion of treated patients completing 4 week, 8 week and 12 week side effect questionnaire
6. Proportion of treatment doses taken as per protocol (adherence)
7. Proportion of treated patients taking at least 90% of their prescribed doses
8. Proportion of treated patients requiring a step down in therapy due to adverse side effects

Clinical/Safety

9. Mean hemoglobin increment at 4 and 12 weeks
10. Proportion with complete hemoglobin response defined as hemoglobin greater than or equal to 120 g/L at 4 weeks and 12 weeks for women and greater than or equal to 130 g/L at 4 weeks and 12 weeks for men.

11. Change in reticulocyte count at 4 and 12 weeks
12. Change in ferritin, serum iron, TSAT at 12 weeks
13. Quality of life (FACT-fatigue scale) at 4, 8 and 12 weeks
14. Proportion with side effects and type of side effects at 4, 8 and 12 weeks
15. Proportion of patients who stop taking oral iron due to side effects at 4 and 12 weeks
16. Need for escalation in therapy (need for alternative oral iron therapy (including if a participant in the every other day group escalates to daily iron), need for intravenous iron, need for transfusion, visit to emergency department related to anemia) at 12 weeks
17. Proportion of patients with a drop in hemoglobin of 10 g/L or more from baseline at weeks 4 and 12

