5.4.1.1 Screening and enrollment will occur within 1 week of randomization

Case logs will be initiated for each referral meeting inclusion criteria, indicating:

- Any applicable exclusion criteria as listed in 5.2.2
- Reason for lack of consent amongst eligible patients
- Protocol violations for enrolled patients

Medical history:

- Demographics: age, sex, height, weight
- Diagnosis (reason for iron deficiency anemia, if known)
 - Example: gynecological, gastrointestinal, urologic, blood donation

- History of observed bleeding in the past 2 months: Y/N
 - Location of bleeding
 - Severity by WHO grade 1-3 (see Appendix A)
 - If menstrual bleeding, use validated tool (see Appendix B)
- Diet
 - Vegetarian
 - Vegan
- Blood Donation: Y/N
 - Number of times in past year?
 - Number of times in past 4 months?
- Comorbidities
 - Rheumatologic disorders: e.g. SLE, rheumatoid arthritis
 - Smoking
- Medication history at time of enrollment
 - Ranitidine
 - Proton pump inhibitor use
 - Medications
 - Other vitamin supplements (not including iron)
- History of oral iron use: Y/N
 - Any iron use in the past year: Y/N
 - If yes, last oral iron intake: (date)
 - Type of oral iron and tolerability
- History of IV iron use in the past year: Y/N
 - Type of IV iron

Questionnaire:

- FACIT-Fatigue scale (see Supporting Documents)

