5.4.2 Follow-up Visits and Assessments

5.4.2.1 Week 1

Participants will be contacted by telephone or email for the following assessment at Day 7 ± 3 days

- Adherence as determined by patient diary (supporting documents)
- Side effect questionnaire (supporting documents)

5.4.2.2 Week 4

Participants will be contacted by telephone or email at Day 28 ± 7 days for the following assessment

- Adherence as determined by patient diary
- Side effect questionnaire
- FACIT-fatigue scale questionnaire
- Medication history (to confirm if any new or discontinued medications)
- Reminder to do laboratory tests (at the local site or local lab) for CBC, reticulocyte count

At the week 4 assessment, if the participant has a drop in hemoglobin of more than 10 g/L from baseline, then the patient will be referred back to the most responsible physician for management and escalation of therapy. If the patient receives escalation of therapy (need for alternative oral iron therapy including if a participant in the every other day group escalates to daily iron, need for intravenous iron, need for transfusion, visit to emergency department related to anemia), the participant will no longer complete any further study assessments and the most responsible physician will be notified. The reason for the drop in hemoglobin will be classified as: ongoing bleeding; non-compliance (defined as less than 50% of pills); other reason; or no clear reason.

5.4.2.3 Week 8

Participants will be contacted by telephone or email at Day 56 ± 7 days for the following assessment

- Adherence as determined by patient diary
- Side effect questionnaire
- FACIT-fatigue scale questionnaire
- Medication history (to confirm if any new or discontinued medications)

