APPENDIX C:

Table 1: Flow Chart of Assessments/Procedures to be Performed Throughout the Study

Procedures	Prior to Enrolment	After Enrolment	Week 1 (±3 days)	Week 4 (±7 days)	Week 8 (±7 days)	Week 12 (±7 days)	Week 13 (7 days ± 3 days after final study visit)
Referring clinician offices identify potential patients as participants	X						
Patient (surrogate) informed consent	X						
Inclusion and exclusion criteria	X						
Randomization		X					
Baseline Data							
Case Logs (reason for lack of consent, protocol violations)	X						
Medical History		X					
Laboratory Assessments							
Hemoglobin	X			X		X	
Reticulocyte Count	X			X		X	
C reactive protein (CRP) – acute phase reactant	X						
Ferritin	X					X	
Serum Iron	X					X	
Transferrin Saturation (TSAT)	X					X	
Creatinine clearance	X						
Subjective Patient Assessments							
FACIT-Fatigue Scale Questionnaire		X		X	X	X	
Patient Diary Adherence			X reminder	X	X	X	
Side Effect Questionnaire				X	X	X	
Pill Count						X	
Adverse and Serious Adverse Events			X	X	X	X	X
Need for Therapy Escalation			X	X	X	X	

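### The side effect outcome has no baseline measurement, and the week 1 questionnaire is required in 5.4.2.1, unticked in Appendix C and unused in item 14

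*Combined protocol and SAP*

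**What the plan says.** **Outcome.** Section 7.2, item 14, reads "Proportion with side effects and type of side effects at 4, 8 and 12 weeks as determined by the oral iron side effect questionnaire". Section 3.4 gives the same three times: "Proportion with side effects and type of side effects at 4, 8 and 12 weeks". The protocol summary also lists gastrointestinal adverse effects at weeks 4, 8 and 12. The matching completion outcome (item 4 in section 7.2, item 5 in section 3.4) counts patients "completing 100% of 4 week, 8 week and 12 week side effect questionnaire".

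**Baseline.** Section 5.4.1.1 lists one questionnaire: "FACIT-Fatigue scale (see Supporting Documents". The nearest related item in the medical history is how well earlier oral iron was tolerated, which is not a record of current symptoms.

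**Week 1.** Section 5.4.2.1, for the contact at day 7 ± 3, lists "Side effect questionnaire (supporting documents". In Appendix C, the row "Side Effect Questionnaire" is ticked at weeks 4, 8 and 12 only.

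**Background.** Section 2.1.6 reports gastrointestinal side effects in 35% (range 10-90%) of patients on ferrous sulfate and "22 % (range 0-69%) in the placebo arms". Section 5.3.4 says "Side effects may improve over the initial 1-2 weeks of oral iron".

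**The concern.** Reducing side effects is part of the rationale in section 2.2 and of the secondary objective in section 3.2. The pilot is also meant to inform the design of the definitive trial (section 8.2). The tolerability outcome therefore needs to be interpretable.

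Two features work against that. First, without a baseline form, a patient who already had constipation or nausea cannot be told apart from one who developed it on iron. Second, the plan gives conflicting instructions on collecting the week 1 form and states no use for it. If some sites follow section 5.4.2.1 and others follow Appendix C, week 1 data will be missing by site. Neither gap can be repaired after the data are collected.

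**Working it through.** **1. Is there a plan figure to reproduce?** None concerns side effects. The sample size rests on hemoglobin. For the Table 2 row with true difference 0, SD 5, margin 5, one-sided alpha 0.05 and 90% power, n per arm = 2 × (1.645 + 1.282)² × 5²/5² = 17.1, rounded up to 18. That gives 36 in total, and 36/0.70 = 51.4, so 52. This matches the plan, and nothing below changes it.

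**2. Where the questionnaire appears.**

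| Place | Baseline | Week 1 | Week 4 | Week 8 | Week 12 |
|---|---|---|---|---|---|
| Sections 5.4.1 and 5.4.2 | no | yes | yes | yes | yes |
| Appendix C | no | no | yes | yes | yes |
| Item 14 (3.4 and 7.2) | no | no | yes | yes | yes |
| Completion outcome | no | no | yes | yes | yes |

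The baseline column is empty throughout. The week 1 column contradicts itself.

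**3. How the outcome is defined.** In section 7.2, items 9, 11 and 12 (hemoglobin, reticulocytes, iron indices) are each the later value minus the baseline value. Item 14 has no baseline reference, and none could be built from the data listed.

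**4. Timing.** The week 1 contact falls on days 4 to 10 (7 ± 3). The week 4 contact falls on days 21 to 35 (28 ± 7). The first one to two weeks end by day 14, so the earliest contact that item 14 uses is at least 7 days later. Section 5.3.4 also lets patients with continuing symptoms step down in frequency, including from daily to every other day. By week 4 some daily-arm patients may therefore be taking iron at the other arm's frequency.

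**5. What else covers the early period.** Adverse events are ticked at week 1 in Appendix C. Item 8 counts step-downs due to side effects without a time limit, and item 15 counts stopping due to side effects at weeks 4 and 12. These are partial. Section 9.1.1 sends only drug-related events to the eCRF. Section 9.2.5 lets the investigator leave out events common in the population, and the trial is open label. Items 8 and 15 register only symptoms that changed treatment.

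**6. Size.** The SD of a chance between-arm difference in the proportion with symptoms at baseline is √(2p(1−p)/n), with n = 26 per arm (section 5.1). The documents do not give p, so these values are assumptions spanning the quoted placebo range:

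- p = 0%: 0 points
- p = 22%: √(2 × 0.22 × 0.78/26) = 11.5 points
- p = 50%: √(2 × 0.50 × 0.50/26) = 13.9 points, the maximum
- p = 69%: √(2 × 0.69 × 0.31/26) = 12.8 points

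Such an imbalance reaches item 14 only if the symptoms persist and the form counts them. The list shows how wide the unknown is; it does not estimate the effect.

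**The case against.** The strongest reply is that this is a secondary outcome of a feasibility pilot, with no side effect hypothesis or power, and that randomization already protects the comparison. Inflammatory bowel disease, celiac disease and recent intolerance of oral iron are excluded, which should lower baseline symptoms. Section 2.1.6 reports no significant association between dose and gastrointestinal side effects. The form is in Supporting Documents that are not part of the text reviewed. It may ask patients to attribute symptoms to iron, and a long recall period at week 4 might recover some of the early period.

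All of this stands as a limit on how large the problem can be said to be. It does not supply a baseline measurement or resolve the conflict between section 5.4.2.1 and Appendix C.

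Three stronger readings are tempting and should not be drawn:

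- **Most reported symptoms are background.** A reader might divide 22% by 35% and conclude that 63% is noise. The 22% is a rate on placebo, with a range of 0-69%. It is not a prevalence before treatment. Symptoms that arise on placebo would still count as new since baseline, so 63% is not the share that a baseline form would remove.
- **Item 14 counts any symptom.** The form's wording is not available, so this cannot be shown.
- **The early period is lost.** It is missing from the questionnaire outcome only. Section 5.4.2.1 collects the form, section 14.2 lists source documents for the week 1 contact and the questionnaire, and step 5 above lists the other partial records.

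**Conclusion.** The point holds as a gap in measurement and a contradiction in the schedule. It is not a claim of bias between arms. Three facts are plain from the text: no side effect questionnaire at baseline, week 1 required in one place and unticked in another, and an outcome that uses neither. Pre-treatment symptoms that the form picks up would inflate the proportion in each arm and add noise to the contrast.

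The size cannot be stated from the documents. It depends on pre-treatment prevalence, on how far symptoms persist, and on the form's attribution wording and recall period. The change is worth making because it is cheap, and because the missing data cannot be recovered later.

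**What to change.** 1. Give the side effect questionnaire at baseline, alongside FACIT-Fatigue, and add it to section 5.4.1.1 and Appendix C.
2. Reconcile Appendix C with section 5.4.2.1 by ticking the questionnaire at week 1.
3. Add week 1 to item 14 and to the questionnaire completion outcome in sections 3.4 and 7.2, and update the protocol summary to match.
4. Report the proportion with symptoms new since baseline alongside the raw proportion. Include worsened symptoms only if the form grades severity. Keep baseline symptom status available for adjustment.
5. State the form's recall period and whether it asks patients to attribute symptoms to iron.

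The cost is one extra short form per patient at a baseline contact that already takes place. Week 1 adds nothing beyond what section 5.4.2.1 already requires. The sample size stays at 52.
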